5. ASSESSMENT AND DERIVATION OF EFFICACY AND BIOMARKER ENDPOINTS

5.1. Primary Efficacy Endpoint

The primary efficacy endpoint will be based on the occurrence of new PEx. The occurrence of a new PEx will be assessed throughout the active dosing period. The primary comparison of the

lenabasum 20 mg BID treatment cohort to the placebo cohort will be based on the event rate of PEx per subject per 28 weeks using the primary definition of PEx.

The event rate comparison is calculated as follows:

$$\theta = R_l / R_p$$

where R_l is the event rate of PEx per subject per 28 weeks using the primary definition of PEx for the lenabasum treatment cohort, and R_p is the event rate of PEx per subject per 28 weeks using the primary definition of PEx for the placebo group.

See [Section 4.2.1](#) for the calculation of the event rate of PEx per subject per 28 weeks.

At screening and again at Visit 1, subjects and/or their legally acceptable representative will be instructed when and how to call the site staff to report new or worsening respiratory or systemic symptoms. Subjects who experience new or worsening respiratory symptoms or have received a prescription for a new antibiotic from a physician other than a study physician should contact the site staff and return for an unscheduled Possible PEx Visit if directed to do so.

At each visit, the investigator will assess the subject for the presence of any new or worsening respiratory symptoms. The physician will assess medical history for changes from last visit, perform physical examination of the lungs and physical examination of other organs as indicated by change in medical history, and complete the AUR-Q (refer to Case Report Form).

The AUR-Q questionnaire includes Fuchs criteria (Fuchs et al, 1994) and a list of additional signs and symptoms, that may have led a physician to make a diagnosis of pulmonary exacerbation. At least 4 out of 12 Fuchs criteria are required to make a diagnosis of a new PEx by the primary definition, but not by the secondary definition.

5.1.1. Primary Definition of New Pulmonary Exacerbation

The derivation for new PEx by the primary definition is provided below. The rules for defining new antibiotics used for new PEx, including the start and stop days, are also provided below.

Primary definition of new PEx:

- Physician diagnosis of PEx
- Prescription of new antibiotics for PEx
- Start date of new antibiotics for PEx is > 28 days after the stop date of any antibiotics given for any previous PEx. The physician does not need to determine if there is > 28 days from last use of antibiotics to the new antibiotics for PEx analysis purposes. The > 28-day gap will be determined centrally
- A new PEx is not defined by the number of antibiotics prescribed or the order or route of administration of the antibiotics (oral or IV) for that new PEx
- ≥ 4 out of 12 Fuchs criteria are met

New antibiotics for PEx

- Must be given for PEx

- Must be administered by oral or IV route
- Start date is day the physician prescribes that the subject should take this antibiotic treatment for a PEx
- Stop date is the last day the physician prescribes that the subject should take this antibiotic treatment for a PEx
- Start day > Day 1
- Start day \leq Day of Visit 8 or discontinuation from the study
- Regularly given prophylactic inhaled, oral, or IV antibiotics do not count as new antibiotics unless the dose is increased or given early for a PEx

Start day of a new PEx:

The first day that the physician prescribes that the subject should take any new antibiotic treatment for that new PEx

Stop day of a new PEx:

The last day that the physician prescribes that the subject should take any new antibiotic treatment for that new PEx or day of discontinuation from the study, whichever is sooner

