5.2. Secondary Efficacy Endpoints

5.2.1. Secondary Definition of Pulmonary Exacerbation

The following derivation is provided for new PEx by the secondary definition. Definitions of new antibiotics for PEx and start and stop days of new PEx are as outlined in [Section 5.1.1](#).

Secondary definition of new PEx:

- Physician diagnosis of PEx
- Prescription of new antibiotics for PEx
- Start date of new antibiotics for PEx is $>$ 28 days after the stop date of any antibiotics given for any previous PEx
- A new PEx is not defined by the number of antibiotics prescribed or the order of route of administration of the antibiotics (oral or IV) for that new PEx

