9.2. Discontinuations, Lost to Follow-up, and Unscheduled Visits

All assessments of efficacy and safety done after discontinuation of study drug will be included in primary efficacy and safety analyses, for subjects who permanently discontinue study product, do not withdraw consent, and continue in the study.

If a subject withdraws consent, their last regularly scheduled study visit before withdrawing consent will be their last visit for efficacy and safety assessments.

If a subject is lost to follow-up, their last regularly scheduled study visit that they attended will be considered their last visit.

Efficacy assessments done at Unscheduled Visits and Possible PEx visits will be counted in efficacy analyses, only if AUQ-R at that visit indicates that the subject is having a PEx that meets primary or secondary definitions of a new PEx. Otherwise, efficacy assessments done at unscheduled visits and Possible PEx visits will be included only in listings.

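### Read literally, SAP 5.1.1 lets a treated PEx with fewer than 4 Fuchs criteria, itself uncounted, remove a following Fuchs-positive PEx from the primary count

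*SAP*

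**What the plan says.** Section 5.1.1 of the SAP lists joint conditions for a primary-definition event. Beyond the physician's diagnosis and a prescription of new antibiotics, two matter here:

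- Severity: "≥ 4 out of 12 Fuchs criteria are met".
- Gap: "Start date of new antibiotics for PEx is > 28 days after the stop date of any antibiotics given for any previous PEx". The gap is applied centrally.

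The antibiotics that start the clock are defined in the same section. The relevant condition is "Must be given for PEx", by the oral or IV route, with no Fuchs requirement. The clock runs from the prescribed stop: "Stop date is the last day the physician prescribes that the subject should take this antibiotic treatment for a PEx".

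The Fuchs threshold belongs to the primary definition alone. Section 5.1 says "At least 4 out of 12 Fuchs criteria are required to make a diagnosis of a new PEx by the primary definition" and adds that the secondary definition does not need it. Section 5.2.1 keeps the same gap rule without the Fuchs criterion and carries over the rest: "Definitions of new antibiotics for PEx and start and stop days of new PEx are as outlined in" Section 5.1.1. A physician-diagnosed, treated episode with 2 or 3 criteria is therefore still a PEx in this SAP.

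**The concern.** The event that starts the clock and the event that is counted are defined differently. Any treated PEx starts the clock, but only one with at least 4 criteria is counted. A mild treated episode followed within weeks by a full exacerbation can then contribute nothing: the first part fails on severity and the second on the gap.

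Three things depend on this rule: the primary endpoint, the 5 mg comparison on the same definition, and both primary-definition time-to-first-PEx endpoints. Under Section 9.5.3 the affected subject would be treated as event-free, unless a later PEx clears the gap. The sensitivity analyses in 9.4.2 change only the population (mITT or PP) and the model (Poisson or negative binomial), so none would show the loss. The exposure denominator in 4.2.1 also keeps the blocked days.

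**Working it through.** **1. A worked case under the literal rule.** Assume a 14-day course.

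- PEx 1: 3 criteria, antibiotics Days 40-53.
- PEx 2: 6 criteria, antibiotics from Day 70.
- Gap = 70 - 53 = 17 days, which is not more than 28.

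| | Fuchs ≥ 4 | Gap > 28 days | Primary | Secondary |
|---|---|---|---|---|
| PEx 1 | no | yes | 0 | 1 |
| PEx 2 | yes | no | 0 | 0 (same episode) |
| Total | | | 0 | 1 |

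The block lasts longer than 28 days. It runs from the first antibiotic day to 28 days after the prescribed stop, here 13 + 28 = 41 days after the start, or 42 calendar days. PEx 2's own antibiotics then extend it.

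**2. The plan's own figure.** Section 6.3 gives 80% power, rate ratio 0.65, control rate 0.80, about 166 per arm and 15% dropout. The treated rate is 0.65 × 0.80 = 0.52, and 166 × 0.85 = 141 per arm. With a Wald test on the log rate ratio:

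power = Φ(|ln 0.65| / √(1/(141 × 0.80) + 1/(141 × 0.52)) − 1.96) = Φ(0.431/0.150 − 1.96) = 81.9%.

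The stated power is reproduced to within 2 points.

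**3. Rough size of the loss.** The SAP gives neither the sub-threshold frequency nor the course length. Assume 14-day courses and 0.2 to 0.4 sub-threshold PEx per 28 weeks.

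- Expected qualifying PEx in one 42-day block at 0.80 per 196 days: 42 × 0.80/196 = 0.171.
- Events lost per subject: 0.171 × 0.2 = 0.034, up to 0.171 × 0.4 = 0.069.
- As a share of 0.80: about 4% to 9%. This is slightly high, because it ignores overlapping blocks.

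**4. Simulated size of the loss.** Onsets are random over 196 days, with 0.9 Fuchs-positive onsets per 28 weeks before merging and 14-day courses. The loss is the literal rule against episode-level counting. Values in brackets are from a repeat with 100,000 subjects per setting.

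| Sub-threshold PEx per 28 weeks | No escalation | 10% escalate | 20% escalate |
|---|---|---|---|
| 0.2 | 3.4% (3.4%) | 5.1% (4.8%) | 6.6% (6.3%) |
| 0.4 | 6.6% (6.5%) | 9.2% (9.6%) | 12.9% (12.1%) |

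Here a sub-threshold episode escalates if it becomes Fuchs-positive within the course or the next 28 days. The escalation rates are assumptions too.

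**5. Direction and power.** The sub-threshold share is the same in both arms. The comparator is a clock started only by Fuchs-positive PEx, with rates set near 0.80 and 0.52 under that comparator. Power is at 141 per arm. Each arrow runs from the comparator to the literal rule.

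| Sub-threshold share | Placebo events lost | 20 mg events lost | Rate ratio | Power |
|---|---|---|---|---|
| 10% | 2.0% | 1.2% | 0.65 → 0.65 | 83% → 81% |
| 20% | 4.3% | 2.7% | 0.65 → 0.66 | 82% → 77% |
| 30% | 7.4% | 4.7% | 0.65 → 0.67 | 81% → 73% |
| 40% | 11.3% | 7.1% | 0.65 → 0.68 | 82% → 69% |

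More events are lost in the arm with more PEx, so the ratio moves toward 1.

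**The case against.** The strongest reply is that a zero count is one reading and not the only one. Section 5.1.1 does not say when the Fuchs criteria must be met. It also says that the number, order and route of antibiotics do not define a new PEx, so one PEx can span several courses. Section 5.1 has an AUR-Q completed at each visit. On that view a later score could qualify the same episode. This stands as far as it goes: an episode-level reading is open, but the SAP does not state it. Nor does it limit the earlier PEx in the gap rule to counted events. Whoever programs the central derivation must choose.

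A reader might take Section 9.2 ("only if AUQ-R at that visit indicates that the subject is having a PEx") as proof that scoring is visit by visit. It is not. That sentence decides which assessments at Unscheduled and Possible PEx Visits enter the efficacy analyses, and it refers back to the definitions. It does not assign Fuchs counts to episodes.

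A reader might also infer a bias in favour of lenabasum, if the drug shifted first presentations below 4 criteria. Nothing in the SAP shows such a shift. If sub-threshold PEx doubled from 0.2 to 0.4 on active drug only, the differential loss would lower the ratio by about 3% without escalation (0.934/0.966 = 0.967) and by about 7% at 20% escalation (0.871/0.934 = 0.933). That is possible but not shown. With equal shares the movement is the other way.

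Two further points stand in part. The 0.80 in 6.3 is stated for the primary endpoint and may already allow for the gap rule, so a shortfall against planned power is not established. The first secondary endpoint does count the episode. But it also counts every mild episode, so a difference between the two definitions would not isolate this loss.

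**Conclusion.** The point holds as a gap in the derivation rule. On the literal text, an uncounted PEx can remove a Fuchs-positive PEx from the primary count, and no other section or planned analysis recovers it. The SAP also leaves open which AUR-Q governs a continuing episode.

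The size is unknown from the document. With 14-day courses and 0.2 to 0.4 sub-threshold PEx per 28 weeks, the loss is about 3-7% of Fuchs-positive episodes under independence, rising to 5-13% if 10-20% of mild episodes escalate. With equal sub-threshold shares, the likely effect is modest attenuation and some loss of power.

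The two definitions are not otherwise inconsistent: they share the gap rule, so primary events are already a subset of secondary events. This should be fixed, but it does not invalidate the endpoint.

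**What to change.** Before unblinding, rewrite the derivation in 5.1.1:

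1. Build episodes from antibiotic courses for PEx separated by 28 days or less.
2. Count an episode once as a primary-definition PEx if any AUR-Q completed within it records at least 4 of 12 Fuchs criteria.
3. State the event date for primary-definition time to first PEx: either the first antibiotic day of the episode or the start of the course at which the criterion is met. The first choice dates some events to a day on which the primary criterion was not yet met, so it should be made openly.
4. Add the literal visit-level rule as a sensitivity analysis for the primary and first secondary-family endpoints that use the primary definition.

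The cost is one derivation rule and its programming, using data already collected. The event count, and possibly some event dates, change slightly. Section 2 closes the SAP to sponsor changes after signature, apart from analyses requested by FDA. The rule should therefore be settled before then or, failing that, documented while still blinded and reported as a change under Section 14.

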5.2. Secondary Efficacy Endpoints

5.2.1. Secondary Definition of Pulmonary Exacerbation

The following derivation is provided for new PEx by the secondary definition. Definitions of new antibiotics for PEx and start and stop days of new PEx are as outlined in [Section 5.1.1](#).

Secondary definition of new PEx:

- Physician diagnosis of PEx
- Prescription of new antibiotics for PEx
- Start date of new antibiotics for PEx is $>$ 28 days after the stop date of any antibiotics given for any previous PEx
- A new PEx is not defined by the number of antibiotics prescribed or the order of route of administration of the antibiotics (oral or IV) for that new PEx

5.2.2. Cystic Fibrosis Questionnaire-Revised Respiratory Domain Score and Other Domain Scores

The CFQ-R is a well-established disease-specific health-related quality of life measure for children, adolescents and adults with CF ([Quittner et al, 2005](#), [Dill et al, 2013](#)). It is a profile measure of health-related quality of life which consists of self-reported items and has proven reliability and validity. The CFQ-R measures functioning in a variety of domains, including Physical Functioning, Vitality, Health Perceptions, Respiratory Symptoms, Treatment Burden, Role Functioning, Emotional Functioning, and Social Functioning.

The Adolescent/Adult version of the CFQ-R will be used for subjects \geq 14 years of age at the time of consent. For subjects ages 12-13 at the time of consent, two versions of the questionnaire will be administered; the Child version for ages 12-13 will be given to the subject, and the Parent/Caregiver version for ages 6-13 will be administered to one of the subject's parents or legal representatives (all efforts should be made to have the same parent fill out this questionnaire at each required study visit, if possible). The subject will be provided the CFQ-R in their native language, if not fluent in English, and will be asked to fill out the questionnaire before other interactions with site staff.

Actual values and change from baseline in all CFQ-R domain scores will be calculated centrally. Change in CFQ-R respiratory domain at Visit 8 is a secondary efficacy endpoint.

Actual values and change from baseline in all CFQ-R domain scores at all visits, except change in CFQ-R respiratory domain score at Visit 8, are tertiary efficacy endpoints.

5.2.3. Forced Expiratory Volume in 1 Second

Spirometry including measurements of FEV1 and FVC will be done at screening, at Visits 1-9 and all Possible PEx Visits. FEV1 is the volume of air that can be blown forcibly out of the lungs in 1 second, after full inspiration. FVC is the amount of air which can be forcibly exhaled from the lungs after taking the deepest breath possible. The FEV1 results will be calculated as % predicted and L (absolute), and FVC results will be calculated as % predicted and L (absolute).

The same equipment and operator should be used for each measurement, for a given subject.

For a given subject, the investigator must determine at Visit 1 whether measurements at all Visits for that subject will be done without bronchodilator pre-treatment or with bronchodilator pre-treatment. The measurements must be done at all Visits for a given subject using a consistent procedure. It is preferred that measurements be done without pre-bronchodilator treatment. In this case, any treatment with short-acting bronchodilators will be held for four hours before the pre-bronchodilator spirometry, unless medically necessary. Some subjects with low FEV1 measurements may not tolerate spirometry without pre-bronchodilator treatment. For these subjects, it is acceptable to pre-treat with a short-acting bronchodilator 10-20 minutes before spirometry. For these subjects, pre-treatment with bronchodilator should be done before every spirometry procedure.

Ideally, FEV1 values will be measured on 3 spirograms of acceptable quality and reproducibility. The largest FEV1 will be reported. Other spirometry values will be taken from the spirogram with the largest FEV1 (e.g., FEF25-75). The calculation of absolute and percent predicted FEV1 and FVC will be done centrally. It is acknowledged that, for subjects with low FEV1 or a PEx, it may not be possible to get 3 spirograms of acceptable quality, in which case the best FEV1, FVC, and other spirometry values will be reported. Blinded FEV1 and FVC data will be reviewed prior to database lock, and any extreme outliers (implausible values) will be identified and excluded from the analyses but displayed in listings

Detailed methods for spirometry will be in a manual provided to each site by Corbus.

Change from baseline in FEV1 % predicted at Visit 8 is a secondary efficacy endpoint.

Actual values and change from baseline in FEV1, FEV1 % predicted, FVC, and FVC % predicted at all visits are tertiary efficacy endpoints, except change in FEV1 % predicted at Visit 8.

6. GENERAL STATISTICAL CONSIDERATIONS

6.1. Reporting Conventions

All data analysis will be performed by Statistics & Data Corporation after the study is completed and the database has been locked. The following reporting conventions will be used:

- Outputs will be provided in rich text format for tables and portable document format for tables, listings, and figures using landscape orientation.
- Data from all study centers will be combined for analysis.

- All study data will be listed by subject, treatment, and visit (as applicable) based on all randomized subjects unless otherwise specified. Additional data listings will be provided as described in the sections for the data analyses.
- Summaries for continuous and ordinal variables will include: the number of observations (n) of observations, arithmetic mean, standard deviation (SD), median, minimum (min), maximum (max). Unless specified in the actual table shells, the mean, median, first quartile, second quartile, third quartile, (interquartile range), the upper and lower limits of the confidence interval (CI) will be displayed to one more decimal place than the original data (derived analysis data). Standard deviation and standard error values will be displayed to two more decimal places than the original data. Minima and maxima will be displayed to the same number of decimal places as the original data. Summaries for discrete variables will include frequency counts and percentages. All percentages will be rounded to one decimal place (i.e., XX.X%).
- The number and percentage of responses will be presented in the form XX (XX.X%), where the percentage is in parentheses. The denominator of all percentages will be number of subjects in the analysis population, unless otherwise stated. When count data are presented, the percent will be suppressed when the count is zero in order to draw attention to the non-zero counts. A row denoted “Missing” will be included in count tabulations where necessary to account for dropouts and missing values. Non-zero percentages will be rounded to one decimal place, except 100% will be displayed without any decimal places.
- The day of the first dose of study product will be defined as Day 1, which is the day of Visit 1. All study days before Day 1 will be calculated as (assessment date – first dose date of study product). The study day on or post Day 1 will be calculated as (assessment date - first dose date of study product + 1).
- Baseline value for comparisons to Visit 1 will be defined as the last non-missing value on or before Visit 1 and before the first dose of study product.
- Change from Baseline will be calculated as the value at post-dose minus the value at pre-dose (Baseline). Differences between treatment cohorts will be calculated as lenabasum minus placebo.
- Listings will be presented for all randomized subjects unless otherwise specified.
- All analyses will be conducted using SAS Version 9.4 or higher.
- The modified intent-to-treat (mITT) population will be the primary population for the efficacy analyses. In addition, supportive analyses using the per protocol population will be conducted for the primary efficacy endpoints and selected secondary endpoints, if relevant.
- All statistical tests will be two-sided with a significance level of 0.05 ($\alpha = 0.05$), unless otherwise specified. All p-values will be rounded to four decimal places; p-values less than 0.0001 will be presented as “<0.0001”; p-values greater than 0.9999 will be presented as “>0.9999.”

6.2. Statistical Hypotheses

Primary Endpoint Hypotheses:

$$H_0: \theta = 1$$

$$H_1: \theta \neq 1$$

where $\theta = R_1 / R_p$,

R_1 is the event rate of PEx per subject per 28 weeks using the primary definition of PEx for the lenabasum treatment cohort, and

R_p is the event rate of PEx per subject per 28 weeks using the primary definition of PEx for the placebo group.

Similar hypotheses will apply to the secondary endpoints, where the null hypothesis is the hypothesis of no difference between the active lenabasum dose and placebo, and the alternative hypothesis is that the active lenabasum group differs from placebo.

6.3. Sample Size and Power Considerations

The study is expected to enroll approximately 415 subjects, with ~166 subjects each in the lenabasum 20 mg BID and placebo BID cohorts and ~83 subjects in the lenabasum 5 mg BID cohort (accounting for an approximate 15% dropout rate). The study provides 80% power to detect a significant difference between the lenabasum 20 mg BID dose and placebo in the primary endpoint (PEx event rate) at a two-sided alpha of 0.05. This is based on an event rate ratio of 0.65 (a 35% event rate reduction in the lenabasum group), when the event rate in the control group is 0.80.

This also provides 90% power to detect a significant difference between lenabasum 20 mg BID and placebo BID in the secondary endpoint of time to first PEx. This is based on an estimate of the probability of an event (PEx) in the placebo group of 0.60, an estimated hazard ratio of 0.60 (risk reduction 0.40), and the probability of an event in the lenabasum group of 0.36.

